4.6.2. Overall Cleansing Assessment

Following completion of the procedure and after each segment has been rated, the blinded colonoscopist will provide a global rating of preparation quality for the entire colon (inclusive of their perception of all segments) using the scale outlined in Section 4.6.1.

4.6.3. Additional Efficacy Measures

In addition, the following data will be collected:

1. Adequacy of preparation according to the blinded colonoscopist. If the preparation was not adequate, the need for re-preparation will be recorded.
2. Start time of colonoscopy
3. Time of cecal intubation

4. Completion time of colonoscopy
5. Impact of preparation quality on surveillance interval
6. Volume of water used to improve visualization (investigator's will need to specify cases where a water immersion technique was utilized)

4.7. Pregnancy

Subjects that are female and of childbearing potential must have a serum pregnancy test done at screening. A positive result will rule out the participation of the subject in the study.

Female study subjects must be surgically sterilized or use oral contraceptives, depot contraceptives, double-barrier method, intrauterine device, or testify that she is monogamous with a vasectomized partner, or practices abstinence and will continue to do so during the duration of study. Subjects practicing abstinence must agree to use an acceptable form of birth control should they become sexually active during the study. Women who are post menopausal (as defined in this section), or have had a partial or total hysterectomy or tubal ligation are not considered of child bearing potential.

Oral contraceptives, hormone implants, and injections should be stable for at least 1 month before the study, until 1 month after colonoscopy.

Menopausal status is defined when menses have been absent for 12 months in a woman of appropriate age (usually 45 to 55 years) who has no other suspected or identified cause of amenorrhea.

If a subject becomes pregnant during the study, the subject must be removed from the study and followed until one month after the end of the pregnancy. A pregnancy will not be recorded as an adverse event.

4.8. Concomitant Medications

The use of concomitant medication will be recorded from 7 days prior to screening until completion of the study, including sedation medications and intravenous fluids administered during colonoscopy. Laxatives should not be used within 72 hours of beginning the study preparation.

5. ADVERSE EVENTS

5.1. Adverse Event Definition and Reporting

An Adverse Event (AE) is any untoward medical occurrence associated with the use of a drug in humans, whether or not considered drug related. An AE can therefore be any unfavorable and unintended sign (including a clinically significant abnormal laboratory finding), symptom, or disease temporally associated with the use of a medicinal (investigational) product. Subjects will be queried for any problems they experienced during and after preparation by site personnel. Any symptom on the symptom scale rated as mild, moderate or severe must be reported as an adverse event. Colonoscopy and biopsy findings are not considered adverse events unless considered by the investigator to be related to the preparation or colonoscopy procedure.

Adverse event collection will commence at the time the patient provides informed consent and conclude 30 days after preparation exposure.

Subjects will be instructed to promptly report adverse events to the Investigator. The Investigator will record date/time of report, date/time of onset, description of the adverse event, severity of adverse event, action(s) taken regarding treatment of the event, action(s) taken regarding study participation, duration of adverse event, and the Investigator's assessment of relationship of adverse event to study preparation.

The Investigator should assess the severity of each adverse event using the following categories:

Grade	Severity	Description
1	Mild	Barely noticeable, does not influence functioning causing no limitations of usual activities
2	Moderate	Makes participant uncomfortable, influences functioning causing some limitations of usual activities
3	Severe	Severe discomfort, treatment needed Severe and undesirable, causing inability to carry out usual Activities
4	Life threatening	Immediate risk of death, Life threatening or disabling (Must be reported as serious adverse event)
5	Fatal	Causes death of the participant (Must be reported as serious adverse event)

The Investigator should assess the relationship to study drug for each adverse event using the following categories:

Categories of Attribution:	Description
UNRELATED	There is no evidence of any causal relationship.
POSSIBLE	There is some evidence to suggest a causal relationship (e.g., the event occurred within a reasonable time after administration of the trial medication). However, the influence of other factors may have contributed to the event (e.g., the subject's clinical condition, other concomitant events).
PROBABLE	There is evidence to suggest a causal relationship, and the influence of other factors is unlikely .
DEFINITE	There is clear evidence to suggest a causal relationship, and other possible contributing factors can be ruled out .

5.2 Expected Adverse Events

BLI4700

Because BLI4700 tablets contain the same active ingredient (sodium sulfate) as SUPREP, a similar adverse event profile is expected. In Phase 3 clinical trials, the most frequent adverse events reported by patients taking SUPREP (reported by >3% of patients) included overall discomfort, abdominal pain and distension, nausea, and vomiting.

PREPOPIK

In Phase 3 clinical trials, the most frequent adverse events reported by patients taking PREPOPIK (reported by >1% of patients) included nausea, vomiting and headache⁴.

6. SERIOUS ADVERSE REACTIONS AND DISCONTINUATION OF STUDY

A Serious Adverse Event (SAE) is any untoward medical occurrence that results in at least one of the following outcomes:

- Results in death
- Is life-threatening
- Requires inpatient hospitalization or prolongation of existing hospitalization
- A persistent or significant incapacity or substantial disruption of the ability to conduct normal life functions
- Is a congenital anomaly/birth defect
- Requires medical or surgical intervention to prevent permanent impairment or damage

SAE collection will coincide with the patient providing informed consent to participate in the study and will conclude 30 days after preparation exposure. Pre-scheduled or elective surgeries (that do not represent a worsening of a pre-existing condition) will not be considered serious adverse events. Should a serious and/or unexpected adverse event occur, the Investigator will notify Braintree Laboratories immediately or no later than 24 hours after gaining knowledge of the event. The Investigator will make a decision regarding continuing study participation, and may request input from Braintree Laboratories. The Investigator will be responsible for recommending or providing the patient with appropriate medical therapy. All patients experiencing serious adverse events will be followed until satisfactory resolution occurs.

Braintree Laboratories must be kept apprised of all follow-up information related to serious adverse events. In addition, Investigators must comply with the SAE reporting requirements of the Institutional Review Board with oversight of the study.

Any serious and/or unexpected adverse events that occur during the study will be reported to Braintree Laboratories as follows:

Contact Telephone Numbers:

Braintree Laboratories and its medical monitor will review the report and determine whether an FDA Form 3500A will also be completed and sent to FDA.

7. INSTITUTIONAL REVIEW BOARD (IRB) AND INFORMED CONSENT

IRB review and approval of the study protocol and Informed Consent Form will be obtained prior to initiation of the study. Amendments to the study protocol and consent form generated during the course of the study will also require IRB approval.

8. MANAGEMENT OF INTERCURRENT EVENTS

8.1. Modification of Protocol

Neither an Investigator nor Braintree Laboratories will modify the protocol without first obtaining the concurrence of the other and the IRB. Investigators that continually violate the protocol or commit a serious violation may be subject to termination from the study. The study may be halted if at any time an Investigator or Braintree Laboratories deems the incidence or severity of adverse events to be unacceptable.

8.2. Subjects Discontinued from the Study

Subjects may be discontinued from the study for any of the following reasons:

- An adverse event requiring discontinuation (including failure to tolerate study medication).
- Female participants who become pregnant during the study period.
- Major protocol deviation from the study design by the subject that is observed or suspected by the Investigator
- Subject chooses to withdraw from the study, for whatever reason.
- Subject is lost to follow-up.
- The Sponsor initiates an early discontinuation of the study.
- The subject is withdrawn at the discretion of the Investigator.

Braintree should be contacted if possible prior to discontinuation of any subject.

8.3 Safety Interim Monitoring – Study Stopping Rule

Adverse event data will be monitored on an ongoing basis. Adverse event terms from the study that are listed in the Common Terminology Criteria for Adverse Events (CTCAE, version 4.0) under the system organ classes (SOCs) of Cardiac Disorders, Renal and Urinary Disorders and Metabolism and Nutrition Disorders will be reviewed as part of the study stopping rule.

Braintree Laboratories will consider stopping the study if ≥ 2 subjects develop the same adverse reaction (based on the MedDRA preferred term) listed in the Cardiac, Renal and Urinary, and Metabolism and Nutrition SOCs of Grade 3, or if a single subject develops one of the listed adverse reactions of Grade 4 or higher.

9. DATA ANALYSIS

9.1. Study Endpoints - Efficacy

Primary efficacy will be assessed on the basis of a binary outcome of overall preparation success or failure. For statistical analyses, the following definition of preparation success and failure will be used:

Definition of successful preparation:

1. Overall Cleansing Assessment by the colonoscopist (Section 4.6.2) of “Excellent” or “Good” and does not satisfy any of the following failure criteria.

Definition of failed preparation:

1. Overall Cleansing Assessment of “Fair” or “Poor” by the colonoscopist
2. Any subject who did not have a colonoscopy based on the Investigator’s assessment of the cleansing (subject report of insufficient fecal output, unclear fecal discharge, etc.) or due to preparation related adverse events.
3. Any subject for whom cleaning was not adequate for evaluation

Unevaluable Subjects:

Subjects who were dispensed a kit but withdrew from the study prior to taking any preparation (including subjects who were disqualified subsequent to Visit 1 based on screening laboratory results) are excluded from the efficacy and safety analyses. Any subject who completely or partially took study preparation but did not have a colonoscopy due to non-preparation related reasons (e.g. lack of insurance, inability to return for colonoscopy) will not be included in the efficacy analyses. All treated subjects will be included in the safety analysis.

Success rate will be analyzed using CMH Chi-square adjusting for the effect of investigator site. The formal hypothesis test result (p-value) for treatment difference will be presented together with a two-sided 95% confidence interval for the difference.

Null Hypothesis $H_0: P_1 - P_2 \leq D_0$ versus Alternative Hypothesis $H_1: P_1 - P_2 > D_0$,

where P_1 is the success probability in the BLI4700 group, P_2 is the success probability in the PREPOPIK group (reference or control group), and D_0 is the acceptable margin of equivalence, which we set equal to -10% .

If necessary, we will pool the smallest centers into a “small-centers” stratum until each treatment arm in the smallest stratum has at least ten subjects.

If the test for non-inferiority is statistically significant, we will conduct a test of the superiority hypothesis:

Null Hypothesis $H_0: P_1 - P_2 \leq 0$ versus Alternative Hypothesis $H_1: P_1 - P_2 > 0$.

The two hypothesis tests are hierarchically structured so that the second test will be conducted only if the first test rejects the hypothesis of inferiority. Thus there is no need to correct the alpha levels of the tests for multiplicity.

Sensitivity analyses will be performed for the primary endpoint based on stratification groups outlined in Section 4.1.2.

Additional efficacy endpoints will include:

- Cleansing score by segment
- Number (%) of excellent preparations overall and by segment
- Adequacy of cleaning and need for re-preparation
- Duration of colonoscopy
- Volume of intraprocedural water needed to irrigate the colon
- Number (%) of procedures that reached the cecum
- Time to cecum

Secondary endpoints will be analyzed in a manner similar to the primary analysis using the CMH test adjusting for site effects for count (percentage) outcomes and two-way ANOVA with terms for treatment, site, and their interaction for continuous responses. No adjustment will be made for multiplicity in testing the secondary endpoints. P values will be presented for hypothesis tests, and two-sided 95% confidence intervals for estimates of treatment effects.

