9.4.2. Modified Intention-to-Treat (mITT) Population

This population consists of all enrolled subjects that took any portion of the study preparation. This population will be utilized for primary and secondary efficacy analyses and all safety analyses.

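### Section 9.1 counts a Good or Excellent rating as a success even when a non-study laxative or enema was used between dose 1 and the colonoscopy

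*Combined protocol and SAP*

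**What the plan says.** Under section 9.1, success is an overall rating of Excellent or Good that "does not satisfy any of the following failure criteria". There are three criteria:

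- Criterion 1: "Overall Cleansing Assessment of “Fair” or “Poor” by the colonoscopist".
- Criterion 2: "Any subject who did not have a colonoscopy based on the Investigator’s assessment of the cleansing", or because of preparation-related adverse events. It applies only when no colonoscopy took place.
- Criterion 3: "Any subject for whom cleaning was not adequate for evaluation".

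Other sections touch on non-study cleansing or on who is analysed:

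- Section 4.8: "Laxatives should not be used within 72 hours of beginning the study preparation". It states no consequence for the endpoint and does not name enemas. It also says: "The use of concomitant medication will be recorded from 7 days prior to screening until completion of the study".
- Section 4.6.3: "If the preparation was not adequate, the need for re-preparation will be recorded". An examination judged adequate therefore triggers no such record.
- Section 9.4.2, the population for the primary analysis: "This population consists of all enrolled subjects that took any portion of the study preparation".
- Section 9.4.3: the per-protocol set drops significant deviations, leaves the list of reasons to the SAP, and is supportive to the ITT and mITT results.
- Sections 9.1 and 9.4.1: the named sensitivity analyses use the stratification groups and the ITT set. Neither is described as rescoring subjects who had extra cleansing.

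**The concern.** The objective in section 2 is to compare two preparations. If a subject's colon was cleaned partly by another agent, a Good rating reflects both agents, but the endpoint credits only the assigned one. Criterion 2 recognises that subjects may report poor output before the procedure, but makes them failures only if the procedure is not done. A subject in the same state who takes something extra and is then examined is judged on the final rating alone.

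In a non-inferiority comparison the direction of such an error matters. If extra cleansing rescues the same proportion of would-be failures in each arm, the arm with more failures gains more successes and the observed difference moves toward zero. That makes it easier to pass the -10% margin when the preparation alone would not. Some use is plausible: subjects take the preparation unsupervised (4.1.3), subjects with constipation or a previous failed preparation are enrolled (4.1.2), and blinding is described for the colonoscopist, not the subject (4.1.2).

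**Working it through.** **Inputs from the protocol.** Margin -10% (9.1); 200 per arm, 90% success in both arms, and non-inferiority declared when the lower bound of a two-sided 95% interval exceeds -10% (9.3).

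**Assumed inputs.** The documents give no rate of extra cleansing. Let s1 and s2 be the shares of would-be failures turned into successes by a non-study agent in the BLI4700 and PREPOPIK arms. True rates without it are set at the margin, 80% and 90%.

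**The plan's own figure.** Per-arm n = (z_alpha + z_beta)² × [p1(1-p1) + p2(1-p2)] / margin².

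- With z = 1.645 and 1.282: 8.564 × 0.18 / 0.01 = 154.2, so 155 per arm and 310 in total, as stated in 9.3.
- That match is at one-sided 5%. The two-sided 95% interval rule (z = 1.960) gives 10.507 × 18 = 189.1, so 190 per arm and 380 in total. The planned 400 covers this.

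**Formulas for the scenarios.**

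- Observed rates: p1 = 0.80 + 0.20 s1 and p2 = 0.90 + 0.10 s2.
- SE = √{[p1(1-p1) + p2(1-p2)] / 200}.
- P(declare non-inferiority) = Φ[(p1 - p2 + 0.10)/SE - 1.96].

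**Equal shares in both arms (s1 = s2 = s).** The difference becomes -0.10 × (1 - s).

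| s | Subjects converted (BLI4700 / PREPOPIK) | Observed rates | Difference | P(declare NI) |
|---|---|---|---|---|
| 0% | 0 / 0 | 80.0% / 90.0% | -10.0 | 2.5% |
| 5% | 2 / 1 | 81.0% / 90.5% | -9.5 | 3.5% |
| 10% | 4 / 2 | 82.0% / 91.0% | -9.0 | 4.8% |
| 20% | 8 / 4 | 84.0% / 92.0% | -8.0 | 9.0% |

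Example at 10%: SE = √[(0.1476 + 0.0819)/200] = 0.0339; 0.01/0.0339 - 1.96 = -1.665; Φ = 4.8%.

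**Unequal shares.** The observed difference is -0.10 + 0.20 s1 - 0.10 s2, so the bias is zero when s2 = 2 × s1 and reverses beyond that.

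- BLI4700 only, 10%: 82% against 90%, P = 8.4%.
- 10% and 20%: 82% against 92%, P = 2.5% (no bias).
- PREPOPIK only, 10%: 80% against 91%, P = 1.2% (conservative).

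**Power cost of rescoring.** Suppose the planned 90% in each arm includes some subjects who had extra cleansing.

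- None rescored: SE = √(0.18/200) = 0.030; 0.10/0.030 - 1.96 = 1.373; power 91.5%.
- 2% per arm rescored (88% against 88%): SE = 0.0325; power 86.8%.
- 5% per arm rescored (85% against 85%): SE = 0.0357; power 80.0%.

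**The case against.** The strongest reply is that the scenario is not one the protocol provides for. No section describes a top-up or enema before the procedure, section 4.8 discourages laxatives, and the route described for insufficient output is no colonoscopy, which is a failure. This stands as a limit on size: the number of such subjects may be very small, and 20% conversion would need about 12 of them. It does not change how one who occurs would be scored.

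A second reply is that the existing failure rules already cover the case, because the Poor grade in 4.6.1 mentions a need for more preparation and criterion 3 covers inadequate cleaning. Both describe the colon as examined. A subject already cleaned by another agent and rated Good meets neither.

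A third is that significant deviations leave the per-protocol set. That may be so. The list of reasons is deferred to SAP text that is not in the documents available, so it cannot be said to omit this case. The per-protocol analysis is supportive in any event, and the mITT result is unaffected.

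A fourth is that counting the rating whatever else was taken is a legitimate treatment-policy choice, under which the 2.5% is not inflated. This is fair: the error rates above apply only if the question is what the assigned preparation achieves by itself. That is the natural reading of section 2, but the protocol does not state the choice.

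A reader might also infer that the rule necessarily pulls the arms together. The documents do not support that. Subjects know their preparation, so equal conversion cannot be presumed, and the unequal-share scenarios show the bias vanishing or reversing.

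**Conclusion.** The point holds as a gap in the scoring rule: under 9.1 and the mITT definition, a subject who used a non-study cleansing agent after dose 1 and was rated Good or Excellent is a success in the primary analysis.

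The size is unknown. With equal conversion shares and true rates of 80% and 90%, the false non-inferiority rate rises from 2.5% to between 3.5% and 9.0% for shares of 5% to 20%. These are illustrations under assumed inputs, not estimates for this trial. It would be wrong to conclude that the non-inferiority test is known to be anti-conservative, or that the protocol permits rescue cleansing. The first depends on how use splits between arms, and the second has no basis in the text. The point is a cheap improvement to the endpoint definition, best settled before unblinding.

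**What to change.** Add a fourth failure criterion to 9.1 and carry it into the SAP: *any subject who received a bowel-cleansing agent other than the assigned study preparation between the start of dose 1 and the colonoscopy, whatever the rating.* In addition:

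- Name the same case as a per-protocol exclusion.
- Report the number of such subjects by arm.
- Confirm that the concomitant-medication record captures enemas as well as laxatives, with the time of use. Section 4.8 does not make this explicit.

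If the sponsor intends a treatment-policy endpoint, it should say so and pre-specify a sensitivity analysis that scores these subjects as failures.

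The change affects only how the outcome is counted, not what care is given. It needs one line of text and, if enemas or times are not already captured, a small addition to the record. Success rates and power would be slightly lower: 86.8% instead of 91.5% if 2% per arm are rescored from 90%, and 80.0% at 5% per arm. The loss would be larger if more subjects were rescored on BLI4700 than on PREPOPIK.

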3.3. Duration of Study

Subject participation in this study will last up to 60 days. A screening visit (Visit 1) should be performed within 30 days of the colonoscopy. Subjects meeting all eligibility criteria during the screening visit will be assigned to receive either BLI4700 or PREPOPIK using a dynamic minimization scheme. Subjects will return to the clinic for Visit 2 on the day of their colonoscopy. A follow up visit (Visit 3) will occur 24-48 hours after colonoscopy. Subjects with abnormal laboratory values and/or ongoing adverse events will have follow-up visits 7 days after colonoscopy (Visit 4) and 30 days after colonoscopy (Visit 5), if needed.

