4.1.2. Treatment Assignment / Blinding

Subjects that meet all eligibility criteria will be assigned to a treatment group by a dynamic minimization scheme⁷ implemented using an automated interactive web response system (IWRS). At the time of enrollment the IWRS will assign a drug kit number for site personnel to dispense to the subject. Subjects will be stratified into one of the following three groups. Subjects meeting Group 1 criteria will be assigned to Group 1 regardless of whether or not they meet the Group 2 criterion.

Group 1: Subjects who meet any of the following criteria:

- Prior diagnosis of constipation (historical or active)
- History of prior failed bowel preparation (inadequate examination)
- Currently taking opioid medications
- Body Mass Index ≥ 35

Group 2: Subjects scheduled for a colonoscopy 12:00 PM or later

Group 3: Subjects not meeting Group 1 or 2 criteria

In this single-blinded study, to ensure an unbiased evaluation of the study preparations, the colonoscopist will not be allowed to perform any study drug related activities (treatment assignment, drug dispensing, return and accountability). Any failure to maintain blinding of the treatment to the colonoscopist will be documented as a

protocol violation. Subjects will be instructed not to discuss their study preparation assignment study staff members.

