9.3. Sample Size

Approximately four hundred (400) subjects will be randomly assigned via the minimization scheme to one of two preparations in a ratio of 1:1 (200 subjects per group) and undergo colonoscopy. Based on prior studies using a similar grading system, the success rate for PREPOPIK is expected to be no greater than 90%⁴. Assuming a similar success rate for BLI4700, a two-sided asymptotic 95% confidence interval for the difference in success rates between groups (BLI4700 – PREPOPIK) will result in a lower CI bound greater than -10%, with probability 90%. This result would establish the non-inferiority of BLI4700 to PREPOPIK for a non-inferiority margin of 10%.

Our sample-size calculations for equivalence tests with a binary outcome use the method of Chow et al⁵. If the PREPOPIK success rate is 90% and the BLI4700 success rate is also 90%, the sample size needed is n=310 (total across both study groups) for a non-inferiority margin of 10% and a target power of 90% with confidence 95%. Thus with n=400 subjects we will attain 80% power even with a dropout rate in excess of 20%.

In randomized studies, the purpose of the stratification is to eliminate the stratification factor from the error term, thereby potentially reducing variability⁶. Moreover, because the trial will use stratification in the design, for consistency we will employ a stratified test in the analysis. The CMH analysis on risk differences, by eliminating center effects, essentially renders the analysis equivalent to that of a single-center study. The sample-size calculation described above assumes a single stratum that is free of between-stratum variability and therefore effectively models the stratified analysis that we will conduct.

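### The primary test adjusts for site but not for the three subject groups used as design strata; adding them would be a small, nearly free gain in efficiency

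*Combined protocol and SAP*

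**What the plan says.** **Design.** Section 3.3 has eligible subjects "assigned to receive either BLI4700 or PREPOPIK using a dynamic minimization scheme". Section 4.1.2 repeats this and names one set of strata: "Subjects will be stratified into one of the following three groups". Group 1 is any of: a constipation diagnosis, a prior failed preparation, current opioid use, or BMI of 35 or more. Group 2 is a colonoscopy at noon or later. Group 3 is everyone else. Neither section says whether site also enters the minimization.

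**Primary analysis.** Section 9.1 states: "Success rate will be analyzed using CMH Chi-square adjusting for the effect of investigator site". The smallest centers are pooled until each arm of the smallest stratum has at least ten subjects. The groups come in only here: "Sensitivity analyses will be performed for the primary endpoint based on stratification groups outlined in Section 4.1.2". For secondary outcomes: "Secondary endpoints will be analyzed in a manner similar to the primary analysis using the CMH test adjusting for site effects" (counts), with an ANOVA on treatment, site and their interaction for continuous responses.

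**Rationale.** Section 9.3 reasons that "because the trial will use stratification in the design, for consistency we will employ a stratified test in the analysis". The next sentence concerns centers only: "The CMH analysis on risk differences, by eliminating center effects", which the section says makes the analysis equivalent to a single-center one.

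**The concern.** Section 9.3 gives the stratified design as the reason for a stratified test, and the only strata the design names are the three groups. The test in 9.1 adjusts for something else. If allocation balances a factor that predicts the outcome and the analysis ignores it, the treatment difference is estimated with the benefit of the balance, but the reported standard error does not reflect it. The interval is then slightly too wide, and some power against the -10% margin is lost.

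The choice also needs to be settled in advance. A site-only interval and a group-adjusted interval could fall on opposite sides of -10%. The plan does make site-only the deciding one, but its own rationale points to the other.

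**Working it through.** **1. The plan's own figures.** Inputs from 9.3: 200 per arm, 90% success in both arms, margin 10%, two-sided 95% interval.

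- SE = √(2 × 0.9 × 0.1 / 200) = 0.030. Power = Φ(0.10/0.030 − 1.96) = Φ(1.373) = 91.5%, consistent with the stated 90% probability at 400 subjects.
- The total of 310 reproduces only at one-sided 5%: (1.645 + 1.282)² × 0.18 / 0.01 = 154.1, so 155 per arm. At one-sided 2.5% it is 189.1, so 190 per arm and 380 in total. That is a separate matter and does not bear on this point.

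**2. Size of the effect by hand.** The documents give no group shares or group success rates, so both are assumed. Let the shares be w, the group success rates p_g and the overall rate p. Take no site differences and exact balance within groups.

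- SE reported when groups are ignored: s0 = √(2p(1−p)/200)
- True SE, also reported when groups are adjusted for: s1 = √(2Σw·p_g(1−p_g)/200)
- Power ignoring groups: Φ((0.10 − 1.96·s0)/s1)
- Power adjusting for groups: Φ(0.10/s1 − 1.96)

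| Case | Shares; success | p | s0 | s1 | Power, ignoring | Power, adjusting | Gain (points) |
|---|---|---|---|---|---|---|---|
| A | .3/.2/.5; .80/.90/.95 | .895 | .0307 | .0300 | 90.9% | 91.6% | +0.7 |
| B | .3/.2/.5; .85/.90/.93 | .900 | .0300 | .0298 | 91.7% | 91.9% | +0.2 |
| C | .4/.2/.4; .75/.88/.95 | .856 | .0351 | .0339 | 82.1% | 83.8% | +1.7 |
| D | .4/.2/.4; .85/.90/.95 | .900 | .0300 | .0297 | 91.8% | 92.1% | +0.3 |

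**3. Simulation with sites.** Settings: 400 subjects, 10 or 15 unequal sites pooled by the ten-per-arm rule, site logit SD 0 to 1.5, 80% biased-coin minimization on groups only or on groups plus site, 10,000 runs per cell. That is 4 cases × 4 SDs × 2 site counts × 2 schemes = 64 cells. The comparator is site-only Mantel-Haenszel (MH) with Sato variance. The alternative is a linear model of success on treatment, pooled site and group, with HC1 robust variance.

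- Power change, additive model: +0.1 to +2.1 points, positive in every cell (groups-only minimization +0.1 to +2.1; groups plus site +0.1 to +2.0).
- By case, with 15 sites and groups-only minimization: A +0.8 to +1.1, B +0.1 to +0.2, D +0.3 to +0.6, C +1.6 to +2.0. At site SD 0 these are +0.8, +0.2, +0.3 and +1.7, close to the hand calculation.
- Groups unrelated to success (.90 in all): −0.2 to 0.0.
- Type I error at a true −10%: site-only 1.9–3.1% (mean 2.5%), additive 2.2–3.2% (mean 2.6%). Superiority false positives at a true zero: 1.9–2.7% and 2.2–2.9%.
- With HC3 variance in place of HC1: −0.6 to +1.3 points.
- Groups in place of site: −5.6 to +2.6 points.
- Site × group MH strata: −1.1 to +1.7 points.

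**4. Separate simulation** (3,000 runs; shares .35/.25/.40; site SD 3 points; sites not pooled). Power with 10 and 20 sites, site-only to additive:

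- no group effect: .906 to .907 and .907 to .908;
- .85/.90/.94: .900 to .900 and .893 to .895;
- .78/.93/.985: .910 to .919 and .901 to .917.

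The last case has overall success of .35 × .78 + .25 × .93 + .40 × .985 = .90, so a very wide spread can gain somewhat more than 1 point even at 90%. At a true −10% this case rejected in 2.7–3.0% (site-only) and 3.0–3.5% (additive). Capping success probabilities at 0.995 made the true difference smaller than 10 points, so these rates should not be read as inflation.

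**5. Full crossing.** With 200 per arm, 10 sites and three equal groups, each cell has 200/10/3 = 6.7 per arm; with 20 sites, 3.3. Both fall below the ten-per-arm rule. With sites pooled and site SD 0.5, power went from .898 to .884 (no group effect, 10 sites), .891 to .880 (B, 20 sites) and .894 to .889 (A, 20 sites).

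**The case against.** The site-only test is valid and pre-specified, and site belongs in it because the site's colonoscopist rates the endpoint (4.6.2). Section 9.1 already plans a sensitivity analysis on the groups. Site may be an unstated minimization factor, in which case 9.1 and 9.3 agree with each other. The 2-point gain comes from a case with about 86% success, below the planning rate, and with HC3 variance the change can be negative. The proposal also replaces the named CMH method with a regression model.

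Most of this stands, and it limits the point to one of efficiency. Two parts do not remove it. A sensitivity analysis does not decide non-inferiority, and its method is not described. Even if site is a minimization factor, the groups remain outside the deciding test, and the simulated gain is nearly the same under either scheme.

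A reader might infer that the primary test is invalid, or that site is the wrong factor and should give way to the groups. The documents and the calculations support neither. Type I error stays near 2.5%, and dropping site could cost up to 5.6 points of power.

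**Conclusion.** The point holds as an inconsistency and a modest loss of efficiency. The named strata are absent from the primary test, while 9.3 appeals to the stratified design. It would go too far to call 9.1 and 9.3 contradictory, because the documents do not list the minimization factors.

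Adding the groups gains about 0 to +1 point of power near 90% success under the mild to fairly strong effects of cases A, B and D. It gains up to about +2 points at about 86% success with strong effects, and costs about 0.2 points or less (HC1) if the groups are not predictive. These sizes rest on assumed group shares, group effects, site numbers and site variation. The textual finding rests on none of them. The change is worth making because it is cheap; the trial's conclusion would not be unsound without it.

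**What to change.** - **9.1:** Keep site, pooled by the existing ten-per-arm rule, and add the three groups as additive terms in the primary risk-difference analysis. One example is an identity-link linear model of success on treatment, pooled site and group, without interactions, with the robust variance type named. Read non-inferiority and superiority from this same analysis. Keep the site-only CMH analysis as a sensitivity analysis.
- **9.3:** Make the sentence on consistency with the design name the same factors.
- **4.1.2:** State whether the IWRS also balances on site.
- **Avoid fully crossed site × group MH strata.** The cells break the ten-per-arm rule. With pooled sites, power usually falls by about 1 to 2 points at 10 to 20 sites, although it can rise where the groups are strongly predictive.
- **Optional:** Repeat in 9.1 the 9.3 rule that the lower bound of the two-sided 95% interval must exceed -10%, and add group terms to the secondary analyses.

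**Cost.** The change needs wording and minor programming. The group is already recorded for allocation and no subjects are added. The real cost is a change of primary estimator from CMH/MH to a regression model. If HC3 is preferred to HC1, the power change against site-only MH is -0.6 to +1.3 points. The choice should be fixed before unblinding.
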